2. INTRODUCTION

Mental health problems are estimated to affect 10-20% of children and adolescents worldwide. Research shows that the prevalence of depression rises sharply after puberty and that over half of depressed adolescents have a recurrent episode within five years.

Mental health literacy can be defined as knowledge and beliefs about mental disorders which help people to prevent, recognise and manage problems. We know that low levels of mental health literacy significantly increase the risk of adolescents developing moderate to severe depression and that improving mental health literacy may be a useful way to reduce the future burden of depression amongst young people.

We have co-adapted with young people, parents, professionals and other stakeholders an existing interactive digital application, originally developed in Indonesia with MRC funding (IMPeTUs MR/R012741/1), to improve mental health literacy and self-management skills, for use in the UK with young people aged 12-14. We have also co-designed an additional third book designed specifically for young people in the UK.

The IMPeTUs intervention includes an immersive story line digital game in which young people play as two characters facing mental health challenges. Their decisions affect the direction of the game and eventual outcomes. This application will allow for UK specific intervention content to be developed and for associated materials to be co-produced with young people, parents, professionals and other stakeholders.

In the current study, we will test whether it is feasible to deliver and evaluate our intervention in education and community settings in the UK. We will randomly allocate 20 young people to receive our intervention and 20 to not receive it and then follow them up 3-months later. We will explore how many young people want to take part in our study (recruitment and retention), how much they use our intervention and what sort of follow-up data they are willing to provide. We will speak to facilitators (n=4-6), young people (n=10) and professionals (n=6-10) about their experiences of receiving and delivering our intervention and parents/guardians (n=6-10) about their their child's experiences with the intervention. We will use these findings to collaboratively design a larger study to explore the costs and impacts of our intervention.

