4. STUDY OBJECTIVES

Aim: To evaluate the feasibility/acceptability of an RCT to assess the clinical and cost effectiveness of our co-adapted intervention.

Objectives:

- To train 4-6 facilitators to deliver our co-adapted intervention.
- To recruit 40 young people (four groups of ten, across four sites) to participate in a trial to evaluate the feasibility of a cluster-randomised controlled trial to determine the clinical and cost-effectiveness of our intervention by quantifying participant recruitment, retention and 3-month follow up rates.
- To determine intervention acceptability and identify from multiple stakeholder perspectives the barriers and facilitators to implementation.

Version: 2 Date: 11/7/2022 UREC ID: 2022-14361-24300

- To examine the applicability (content-validity) and acceptability (full and partial completion rates, sensitivity to change) of proposed trial outcome measures and the need for additional CYP prioritised outcomes.
- To collect outcome data to inform parameters for a fully-powered trial, including the identification and standard deviation of the proposed outcomes measure needed to estimate trial sample size.
- To co-produce with stakeholders a protocol for definitive evaluation of our intervention.

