5. STUDY DESIGN AND PROTOCOL

The MRC recommends feasibility testing to ensure new interventions can be implemented prior to undertaking definitive evaluations through fully powered randomised controlled trials [44].

Design: A multi-site, cluster-randomised feasibility trial with nested process evaluation.

Target population: 40 CYP aged 12-14, attending school and community settings (study sites) in Greater Manchester. This age range was chosen following PPI consultation as it corresponds to key stage 3 in the UK educational system, is pre-exam curriculum stage and is relevant in terms of mental illness prevention as the peak period of onset is in the mid to late teens. Parents/guardians (n=6-10), professionals (n=6-10) and facilitators (n=4-6) will also participate alongside CYP participants in the nested process evaluation.

Participants must have capacity to consent (checked at each assessment point) and be able to read and write in English to engage with study materials. Translation of materials is not possible in the current study but will be prioritised in a future study should our intervention show promise. CYP participants need to have access to a smartphone/tablet to use the intervention.

Setting: Education and community settings in Greater Manchester.

Sample size: Our feasibility trial will not formally test intervention effect so a formal power calculation is not appropriate. Instead, sample size has been selected to allow us to assess key feasibility outcomes (recruitment, retention, intervention uptake) and to allow sufficient replications of the study protocol to highlight barriers to completion in the main trial. The sample size will also allow us to estimate differences in means for intervention outcomes to within 0.25 standard deviations.

Recruitment: Four sites (schools/ community venues) will be recruited to the study. All eligible CYP in participating sites will be invited to take part. Educational professionals and community leaders (facilitators) will issue study information to potential participants and obtain CYP assent and parental consent and contact information and collect CYP baseline measures. Direct invitations and information sheets will be available at participating sites so that interested participants can enquire about the study directly.

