Randomisation: In this study, an equal number of clusters (two per arm) will be allocated to the intervention and control arms. This will be achieved by using a blocked randomisation list. The study statistician will produce the randomisation list. A cluster will not be allocated until the full set of 10 participants have been recruited at that cluster, to prevent allocation bias. The allocation

Version: 2 Date: 11/7/2022 UREC ID: 2022-14361-24300

sequence will not be revealed to the other study investigators. Outcome data will predominantly be self-report.

Intervention: Our intervention combines an interactive individual game in conjunction with prepost facilitated group discussions. Our candidate intervention will be co-adapted in phase 1 and additional content and materials co-produced with a range of stakeholders including CYP, parents, professionals and community members.

Group-delivery is a low-cost delivery model which can derive additional benefits through peer-topeer support. Systematic review and meta-analysis [49-50] suggests that engaging students in activities such as games, simulations and group work is more effective than relying solely on didactic methods. We will align the structure of our intervention with current evidence [51-53] supporting the effectiveness of short-term programmes for mental health education and mental health first-aid. Frequency, duration and content of the intervention will be recorded by facilitators and reviewed in phase 2 facilitator and CYP interviews to explore whether treatment was delivered as intended.

Minimum levels of intervention require engagement in each of the chapters of the intervention for a minimum of 1 h each and participation in a facilitated group session before and after the intervention (minimum 5-6 hours in total).

The intervention will provide a range of techniques to improve mental health literacy and promote self-management, e.g. cognitive reframing, distraction and/or the substitution of more adaptive behaviours. Intervention content will be standardised via a manual. Intervention facilitators health and community workers will be trained by a multidisciplinary team, comprising co-applicants [name], [name] and a PPI representative.

Fidelity: Frequency, amount and content of the intervention will be recorded by the facilitators and reviewed in CYP interviews to explore whether treatment is delivered as intended.

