Comparator: Our comparator is assessment only. We will ascertain the range and variability in usual care. The frequency, amount and type of health services accessed by intervention and control arm participants will also be recorded. The control group will be offered access to the intervention at study end.

Feasibility outcomes: The primary outcomes are feasibility outcomes. We will assess CYP recruitment and retention rates, intervention uptake and engagement rates, and the variability and potential floor/ceiling effects in our proposed patient outcome measures. CYP outcomes will be measured as baseline (prior to randomisation), post-intervention (or at approximately 6 weeks post-randomisation for control group participants) and 3-month follow-up.

Clinical outcomes: The primary clinical outcome measure will be a version of the mental health literacy scale, the Knowledge and Attitudes to Mental Health Scale (KAMHS). Additional measures will include the short version of the Mood and Feeling Questionnaire (MFQ), the World Health Organisation Five Well-Being Index (WHO-5), the Revised Children's Anxiety and Depression Scale (RCADS), the Family Cohesion and Satisfaction with Communication subscales of the Family Adaptability and Cohesion Evaluation Scale (FACESIV), and the SF-36

Version: 2 Date: 11/7/2022 UREC ID: 2022-14361-24300

quality of life questionnaire. We will assess the feasibility of these different outcome measures as part of our feasibility trial.

At baseline, CYP demographics and psychiatric history will be recorded.

Analysis: As this is a feasibility trial, analysis will be mostly descriptive.

We will identify the number of study referrals, consents to research contact, and calculate cumulative and monthly recruitment rates. We will examine referral and recruitment rates between different sites (e.g. education and community settings) and recruitment routes (e.g. professional or self-referral).

The proportions of target sample size achieved, of participants who start and engage in the intervention, and the proportion retained in the study and providing outcome data will be calculated. Descriptive statistics will assess the completeness and variability of participant and cost outcome measures at each point.

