6. STUDY PARTICIPANTS

Inclusion criteria:

CYP- Aged 12-14 years attending school and community settings (study sites) in Greater Manchester. Young people will also need access to a smartphone/ tablet to use the intervention.

Professionals/facilitators- Those working with CYP taking part in the evaluation of the intervention

Parents/guardians- Those whose children are taking part in the evaluation of the intervention

Exclusion criteria:

Those unable to give informed consent/assent.

Recruitment:

Facilitators will identify eligible CYP participants and issue direct invitations to these participants to be part of the trial. The direct invitation will either inform the CYP to contact the facilitator (a staff member of the study site) for further information (for an information pack) about the study or

Version: 2 Date: 11/7/2022 UREC ID: 2022-14361-24300

already include an information pack about the study. The information pack will include a contact details form, and information sheets and assent/consent forms for both CYP and their parent/guardian for completion.

In the two study sites of the intervention arm, facilitators will identify professionals who work directly or indirectly with the CYP taking part in the evaluations of the intervention, and issue direct invitations to these individuals to be part of the interview/focus group discussion. Parents/guardians of the CYP in the intervention arm will also be sent direct invitations to be part of the interview/focus group discussion. Again, potential participants will then be issued with consent forms, information sheets and contact details forms.

Participants who withdraw consent:

Participants can leave the study at any time for any reason if they wish to do so without any consequences. If a participant wishes to withdraw from the intervention, we will ask whether they would be happy for us to continue to collect outcome data from them, again making it clear that there will be no negative consequences should they decline. As the statistical analysis is planned according to intention to treat principle, participants that discontinue the intervention but still provide outcome data will be included in the analysis in the group that they were allocated to.

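### No site mix is fixed and allocation is not stratified by setting, so delivery in either education or community settings may never be observed within the evaluated trial

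*Protocol*

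**What the plan says.** Section 2 of the protocol states the question: "we will test whether it is feasible to deliver and evaluate our intervention in education and community settings in the UK". Section 5 repeats the scope: "Setting: Education and community settings in Greater Manchester".

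The Recruitment paragraph of Section 5 describes the sites only as follows: "Four sites (schools/ community venues) will be recruited to the study". Section 4 gives the structure: "To recruit 40 young people (four groups of ten, across four sites". Neither says how many sites of each kind there will be.

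On allocation, Section 5 says that "an equal number of clusters (two per arm) will be allocated to the intervention and control arms", and then: "This will be achieved by using a blocked randomisation list". It gives no block size and mentions no stratification, pairing or other constraint by setting. A cluster is allocated only once its ten participants are in.

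Several sources of evidence come from the intervention sites alone:
- the uptake criterion and the intervention-arm retention criterion (Section 5, feasibility success criteria);
- the facilitators' record of what was delivered (Section 5, Fidelity);
- the professionals and parents approached for interview. Section 6 says of the professionals: "In the two study sites of the intervention arm, facilitators will identify professionals who work directly or indirectly with the CYP". It limits parents to those with a child in the intervention arm.

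Control sites are offered the intervention after the study ends (Section 5, Comparator).

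**The concern.** A trial that asks whether an intervention can be delivered in two kinds of setting needs to see it delivered in both. Here delivery is seen at two sites, and nothing in the protocol makes those two differ in kind. If both are schools, the trial learns nothing about uptake, fidelity or implementation barriers in community venues, and the reverse holds if both are community venues. A green result on uptake would then speak for one setting while the definitive trial was being planned for two. No later analysis can recover this, because the data would not exist. For the same reason the matter cannot be left to an analysis plan: site mix and allocation are settled before any data are analysed.

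A second consequence concerns the exploratory comparison of arms. If the two intervention sites are of one kind and the two control sites of the other, any difference between arms is equally a difference between settings.

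**Working it through.** **Inputs from the protocol.** Four sites of ten (Sections 4 and 5), two per arm (Section 5). Check: 4 × 10 = 40, the stated total, and 2 × 10 = 20 per arm. The protocol gives no probability for the split of settings between arms.

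**Assumptions.** The site mix and the block size are not stated. I take both kinds of site to be present (S = school, C = community venue) and show each possible mix and two block sizes. A failure is an allocation whose intervention arm has no site of one kind.

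**Single block of four.** The number of ways to choose two intervention sites from four is C(4,2) = 6, all equally likely.
- Two S and two C: the failures are {S,S} and {C,C}, so 2/6 = 33%.
- Three of one kind and one of the other: the lone site is a control in C(3,2) = 3 allocations, so 3/6 = 50%.

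**Blocks of two.** One of the first two sites and one of the last two go to intervention, giving 2 × 2 = 4 allocations for a given site order.
- Two-plus-two in order SSCC or CCSS: every allocation has one of each kind, so 0/4 = 0.
- Two-plus-two in any of the other four orders (such as SCSC): 2/4 = 1/2.
- Average over the six orders: (2 × 0 + 4 × 1/2)/6 = 1/3.
- Three-plus-one in any order: 2/4 = 1/2.

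**Four of one kind.** The other setting is certain to be missed, but through recruitment and not through randomisation.

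**Overlap of arm and setting.** In a two-plus-two failure, one arm holds both schools and the other both community venues, so arm and setting coincide completely. In a three-plus-one failure, the intervention arm holds two sites of the common kind and the control arm holds one of each, so the overlap is partial.

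**After the change.** With two S and two C, and one of each randomised to each arm, all 2 × 2 = 4 allocations have both kinds in the intervention arm, so the risk is 0. Stratifying without fixing the mix does not achieve this: in a three-plus-one mix the lone site still goes to control with probability 1/2.

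**The case against.** The best reply is that the protocol never promises results by setting. Its objectives and progression criteria are pooled, and the wording on sites can be read as a pool of eligible venues. The comparisons of arms are called exploratory and underpowered, and with two clusters per arm site differences are mixed with arm under any scheme. Even after the change, delivery in each setting would rest on one site of about ten young people. All of this is fair, and it limits how much the change can buy. It does not remove the point: Section 2 names both settings in the question, and one site of a kind tells the team something about delivery there while none tells them nothing.

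Some stronger readings are tempting, but the documents do not support them.
- *That one third is a floor.* It holds for a single block of four or as an average over random order. The block size is not given, and with blocks of two and a favourable order the risk in a two-plus-two mix is 0.
- *That arm and setting are fully confounded whenever a setting is missed.* This is true only of the two-plus-two failures.
- *That the planned comparison by setting is spoiled.* The protocol says "We will examine referral and recruitment rates between different sites (e.g. education and community settings" and so on. That concerns referral and recruitment, which are complete at a site before it is allocated.
- *That one setting would never receive the intervention.* Controls are offered it at study end, although outside the evaluation.
- *That the protocol decides to disregard setting.* It is silent. The list it describes simply does not secure one site of each kind per arm.

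**Conclusion.** The point holds as a design weakness that is cheap to remove. As written, the plan can leave delivery in one of its two named settings unobserved within the evaluated trial. The chance is 33% for a two-plus-two mix and 50% for three-plus-one, given a single block of four or averaging over random site order. With blocks of two and a known order in a two-plus-two mix it is 0 or 1/2. These figures assume that both kinds of site are recruited and that no unstated constraint is applied when the list is made.

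Where it happens, the uptake and intervention-arm retention criteria, the fidelity records and the intervention-arm process evaluation speak for one setting. Control sites of the other kind would still inform recruitment and completeness of outcome data there.

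**What to change.** In Recruitment, state that two education sites and two community sites will be recruited. In Randomisation, state that allocation is within setting, with one intervention and one control site in each. Both sentences are needed, since stratification does not help a three-plus-one mix. Preferably, allocate the two sites of a setting together once both have completed recruitment. Otherwise the first allocation in a pair reveals the second.

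The cost is two sentences and a different randomisation list, with no more sites or participants. The site mix has to be managed, and a site that recruits quickly may wait for its partner. In a study that Section 16 describes as lasting 12 months, with follow-up at 3 months, one slow site could hold up two of the four clusters, so the timetable should allow for this.

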We will undertake exploratory comparisons of intervention outcomes on an intention-to-treat basis, recognising that these analyses will be underpowered. These will focus on plausible ranges for effect sizes as indicated by 95% confidence intervals, and will be analysed with adjustment for the corresponding baseline measure of the outcome, in order to improve precision. We will attempt to control for clustering in this analysis by including a random intercept in a mixed model, although the small sample size may prove prohibitive. If this analysis can not be realised, we will adjust for site as a fixed effect. We will also present an adjusted mean difference (95% CI) based on ANCOVA (adjusted for corresponding baseline value of the outcome, with no adjustment for site).

Feasibility success criteria: See success criteria outlined below:

Progression criterion: Willingness of participants to be randomised

- Red: Recruit < 60% of required sample.
- Amber: Recruit 60-80% of required sample.
- Green: Recruitment > 80%.

Progression criterion: Retention in intervention arm

Participants will be considered retained in the intervention arm if they are available for assessment at 3 month follow-up.

- Red: Retain < 60% of participants in the intervention arm at 3-month follow-up
- Amber: Retain 60-80% of participants in the intervention arm at 3-month follow-up
- Green: Retain > 80% of participants in the intervention arm at 3-month follow-up.

Progression criteria: Uptake of intervention

Participants will be considered to have suitably engaged with the intervention if they take part in each of the chapters of the intervention for a minimum of 1 h each and participate in a facilitated group session before and after the intervention (minimum 5-6 hours in total).

Version: 2 Date: 11/7/2022 UREC ID: 2022-14361-24300

- Red: Engage <60% of participants at the requisite level described above.
- Amber: Engage 60-80% of participants at the requisite level described above.
- Green: Engage >80% of participants at the requisite level described above.

Process Evaluation: We will use the MRC process evaluation model [44] to explore the delivery and reach of our intervention and understand barriers/enablers to roll-out.

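### The fallback of adjusting for site as a fixed effect cannot estimate the intervention effect, because each site lies wholly within one arm

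*Protocol*

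**What the plan says.** The design is stated consistently in the operative sections of the protocol.

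- Section 4: "To recruit 40 young people (four groups of ten, across four sites".
- Section 5, Recruitment: "Four sites (schools/ community venues) will be recruited to the study".
- Section 5, Randomisation: "an equal number of clusters (two per arm) will be allocated to the intervention and control arms", and "A cluster will not be allocated until the full set of 10 participants have been recruited at that cluster".
- Section 6, Recruitment, refers to whole sites as belonging to an arm: "In the two study sites of the intervention arm".

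The Analysis part of Section 5 then sets out three routes to a between-arm comparison, each adjusted for the baseline value of the outcome. The first choice handles clustering by "including a random intercept in a mixed model, although the small sample size may prove prohibitive". The second is the fallback: "If this analysis can not be realised, we will adjust for site as a fixed effect". The third, presented in any case, is "ANCOVA (adjusted for corresponding baseline value of the outcome, with no adjustment for site". The stated focus of these comparisons is the range of plausible effects shown by 95% confidence intervals.

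**The concern.** Adjusting for site as a fixed effect is sound when participants are randomised individually within sites, because each site then holds both arms. Here the site is the unit that is randomised. All ten participants at a site are in the same arm, so no comparison between arms exists within any site. Once the site means are fitted freely, nothing is left from which to estimate an arm effect.

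This is a stated rule that cannot deliver what it is there for, so it is more than a detail left to the SAP. A SAP that follows the protocol would inherit it. If the fallback were invoked, the analyst would get either no arm estimate or a number that depends on how the software resolves the redundancy. The report would then have no estimate of the intervention effect that allows for clustering.

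**Working it through.** **Inputs.** Four sites, ten participants each, two sites per arm (Sections 4, 5 and 6). Baseline covariate in every model (Section 5, Analysis). The protocol gives no intracluster correlation (ICC), so values of 0.02, 0.05 and 0.10 are assumed below. It states no figure on this point, so there is nothing to reproduce first.

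**Step 1: algebra.** Label the control sites A and B and the intervention sites C and D, with A as reference. The fallback model is

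y = μ + δ·arm + γB·B + γC·C + γD·D + β·baseline + error.

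Because arm = C + D for every participant, replacing δ by δ + k, γC by γC − k and γD by γD − k leaves every fitted value unchanged, for any k. The data cannot distinguish one δ from another, and more participants per site would not help.

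**Step 2: numerical check.** The 40-row design matrix (intercept, arm, three site indicators, baseline) has 6 columns and rank 5. The arm coefficient does not lie in the row space, so it is not estimable.

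**Step 3: what might be printed.** One dataset was simulated with a true arm effect of 0.30. The baseline-adjusted site effects relative to A were B = 0.504, C = 0.013 and D = 1.026. Omitting one further site indicator besides the reference gave:

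| Indicators omitted | Arm coefficient | What it is |
|---|---|---|
| A and C | 0.01 | C − A |
| A and D | 1.03 | D − A |
| B and C | 0.013 − 0.504 = −0.49 | C − B |
| B and D | 1.026 − 0.504 = 0.52 | D − B |

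If both omitted indicators belong to the same arm, the model stays singular (rank 4 of 5 columns). A generalised-inverse fit gave 0.35 with reference coding and 0.03 with sum coding; neither is a one-site-versus-one-site difference. The values are illustrative only. The evidence is the rank deficiency.

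**Step 4: what remains if the mixed model fails.** The share of simulated trials (4,000 per ICC, no true effect, no baseline covariate) in which a two-sided 5% test rejected was:

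| Assumed ICC | Mean of two site means per arm, SE from within-site variation | Two-sample analogue of the no-site ANCOVA | Cluster-level t test, 2 df |
|---|---|---|---|
| 0.02 | 7% | 7% | 5% |
| 0.05 | 11% | 11% | 5% |
| 0.10 | 17% | 15% | 5% |

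The first column is the natural attempt to rescue the fixed-site model by averaging its site effects within arm. That contrast can be computed (0.27 in the dataset above), but its standard error ignores variation between sites.

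**Step 5: width of a valid interval.** Without baseline adjustment, SE = √(2/20) × √(1 + 9·ICC) in SD units. At ICC 0.05 this is 0.316 × √1.45 = 0.381. The t multiplier on 2 df is about 4.30, so the half-width is about 1.64 SD. At ICC 0.02 and 0.10 it is about 1.48 and 1.88 SD. With no clustering and 38 df, the half-width would be 0.64 SD.

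**The case against.** The strongest reply concerns weight, since the algebra is not in dispute. Section 5 says the trial does not formally test the intervention effect, makes feasibility outcomes primary, and calls these comparisons exploratory and underpowered. The three progression criteria (recruitment, retention and uptake) use no effect estimate. Section 4 names the outcome's standard deviation, and not the arm difference, as the quantity needed for the definitive sample size. All of this stands and limits the seriousness of the point.

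The ANCOVA without site is also a partial answer, because it does give an identified arm estimate. It does not replace the fallback, whose purpose is to deal with clustering.

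Some stronger readings are tempting, and the document does not support them:

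- *Any printed figure is one site minus one site.* That is so under usual dummy coding. As Step 3 shows, other solvers give other arbitrary values, and the arm term may instead be dropped or flagged. Section 8 names SPSS, but no SPSS procedure was tested.
- *The fallback will probably be used.* The protocol says only that sample size might prevent the mixed model. It gives no failure rate. A zero site-variance estimate is still a fitted model and would not by itself trigger the fallback.
- *The definitive trial will be misdesigned.* No planned decision is tied to the fallback estimate.

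A reader might also take the Introduction's statement about allocating 20 and 20 young people as individual randomisation, which would rescue the fallback. Sections 4, 5 and 6 rule that out.

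**Conclusion.** The fallback is wrong as written. Site is nested in arm, so the fixed-site model has rank 5 with 6 columns and identifies no intervention effect, whatever the sample size. This rests only on the stated design and on no assumed value.

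The consequence is bounded. It arises only if the mixed model cannot be fitted, which the protocol itself regards as possible. The sole identified estimate would then be the ANCOVA without site, whose 95% interval is too narrow to the extent that outcomes correlate within site. Under assumed ICCs of 0.02 to 0.10, its unadjusted analogue rejected a true null about 7% to 15% of the time instead of 5%. Because the comparison is exploratory and feeds no progression criterion, this is a should-fix and not a fatal flaw.

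**What to change.** Delete the sentence that names the fixed-site fallback. In its place, state that if the mixed model cannot be fitted, one of the following will be done:

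- baseline-adjusted site means will be compared, two against two, with a 95% confidence interval from a t distribution on 2 degrees of freedom; or
- descriptive summaries by site and by arm will be given instead.

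In either case, keep the ANCOVA if wanted, but label its confidence interval as not accounting for clustering. Without that label, descriptive summaries would sit beside an interval that looks like a valid between-arm result.

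The cost is a short change to the protocol, carried into the SAP, with no extra data. The downside of the cluster-level comparison is a very wide interval: a half-width of roughly 1.5 to 1.9 SD before baseline adjustment at the assumed ICCs. That width reflects how little four clusters can say about the effect.
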